Total knee arthroplasty (TKA) can be associated with a large amount of postoperative pain. This pain can oftentimes be severe enough to limit participation in physical therapy and ultimately delay discharge resulting in increased cost. Several strategies have been developed in an effort to decrease postoperative pain following TKA while maintaining lower extremity strength and maximizing participation in physical therapy. Recently, adductor canal blockade has gained popularity as it is reported to provide analgesia to the anterior knee without resulting in significant quadriceps muscle weakness. However, few studies have carefully evaluated the impact of volume of injection of local anesthetic into the adductor canal on motor weakness or pain control. The ability to achieve similar pain control with decreased volumes of local anesthetic would allow the surgery team to apply more local anesthetic to posterior knee structures. Decreased volumes of local anesthetic may also be associated with a decreased risk of local anesthetic toxicity. This study aims to carefully evaluate this relationship using a physical therapy evaluation method that relies on both motor strength and pain control. In addition, we hope to carefully evaluate motor strength using a novel method of strength measurement in an effort to further evaluate the impact of volume of injection of local anesthetic into the adductor canal on motor strength.

Table of contents

List of abbreviations and definitions	7
1. Introduction	8
1.1 Background.....	8
1.2 Rationale and hypothesis	9
2. Objectives	9
2.1 Primary outcome and endpoint	9
2.2 Secondary outcomes and endpoints	9
3. Study design.....	10
4. Study population	10
4.1 Inclusion criteria	10
4.2 Exclusion criteria	10
4.3 Protected populations.....	11
5. Trial interventions.....	11
5.3 Allocation to intervention	11
6. Subject recruitment and consent	12
6.1 Subject identification	12
6.3 Recruitment and consent	12
7. Activities and measurements	12
7.3 Data entry.....	14
7.4 Subject withdrawals	15
8. Data analysis and statistical considerations	15
8.1 Sample size determination	16
9. Risks and benefits of trial participation	16
9.1 Potential risks	16
9.2 Mitigation of potential risks	16
9.3 Potential benefits and risk-to-benefit ratio.....	17
10. Adverse events and unanticipated problems	17
10.1 Adverse event definitions.....	17
10.2 Severity assessment	18
10.3 Causality assessment.....	18
10.4 Procedures for recording and reporting adverse events	18
10.5 Other reportable events.....	18
11. Trial safety monitoring.....	19
11.2 Data Safety Monitoring Committee	19
12. Administrative requirements.....	20
12.1 Good clinical practice	20
12.2 Data quality assurance	20
12.4 Study monitoring.....	20
12.5 Ethical consideration	20
12.6 Patient confidentiality	20
12.7 Investigator compliance	20
12.8 Subject cost and payment	21
13. Funding sources.....	21
References	21

Schedule of activities

	Screening Visit 1	Procedure Visit 2	Post-Adductor Block Visit 3	PACU Visit 4	24-hours Post-op Visit 5	48-hours Post-op Visit 6
Window	Up to 60 days before surgery	Morning of Surgery	15 minutes after adductor block placed +/- 10 mins	Following surgical procedure	24 hours post-op +/- 6 hours	48 hours post-op +/- 6 hours
Screening and Eligibility	X	X				
Informed Consent	X	X				
Demographics	X	X				
Medical History	X	X				
Quadricep motor strength and adductor strength assessment (Kiio sensor)		X	X			
Sensory Leg Exam ¹		X	X			
Questionnaires and Scores ²	SOC	SOC				
Pain Questionnaire ³				X	X	X
Physical Therapy Assessment and Walk Test ⁴					X	X
Concomitant Medications ⁵	X	X	X	X	X	X
Adverse Events	X	X	X	X	X	X

¹Temperature and Sensation will be examined using a pinprick and cold sensory technique

² SF12 mental component and physical component, WOMAC and Knee Society Score, UCLA activity score, range of motion (and degree of varus/valgus deformity will be collected

³ Pain at rest, pain with activity, opioid consumption, nausea, pain disturbing sleep, location of most severe pain and satisfaction with regional anesthesia technique will be assessed

⁴ Pain with physical therapy, quadriceps strength, passive flexion/extension range of motion, postoperative quadriceps strength, postoperative adductor strength, and 10 meter walk test (gait velocity) using Kiio sensor

⁵ Medications that are taken at home regularly and prior to arrival on the day of surgery, surgery premedication, and all medications for nausea and pain will be recorded.

[List of abbreviations and definitions](#)

AE	Adverse event
CFNB	Continuous Femoral Nerve Blockade
CACNB	Continuous Adductor Canal Nerve Blockade
DSMC	Data Safety Monitoring Committee
PACU	Post-Anesthesia Care Unit
POD	Post-Operative Day
SAE	Serious Adverse Event
SSFNB	Single Shot Femoral Nerve Block
SSACNB	Single Shot Adductor Canal Nerve Block
TKA	Total Knee Arthroplasty

1. Introduction

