2.2 Secondary outcomes and endpoints

The secondary purposes of this study are to compare the following perioperative variables:

Pre/Intraoperative Variables:

- Opioid consumption
- Sensory blockade
- Patient perceived discomfort with procedure
- Preoperative quadriceps strength
- Preoperative adductor strength
- SF12 mental component and physical component
- WOMAC and Knee Society Score
- UCLA activity score
- Preoperative range of motion
- Degree of varus/valgus deformity.

PACU Variables:

- Pain
- Opioid consumption
- Nausea
- Time in PACU (duration)
- Satisfaction with regional anesthesia
- Location of most severe pain

Floor Variables:

- Pain at rest
- Pain with activity
- Opioid consumption
- Nausea
- Duration of hospitalization

- Pain disturbing sleep
- Location of most severe pain
- Satisfaction with regional anesthesia

PT Variables:

- Pain with physical therapy
- Quadriceps strength
- Passive flexion/extension range of motion
- Postoperative quadriceps strength
- Postoperative adductor strength

3. Study design

This study is a prospective, single-center, randomized trial in which 60 subjects will be enrolled at the University of Wisconsin Hospitals and Clinics (UWHC). These subjects must meet study eligibility criteria and be scheduled to undergo an elective total knee arthroplasty. These subjects must also agree to undergo neuraxial anesthesia as the primary anesthetic for their surgical procedure and agree to an adductor canal block for postoperative analgesia. Patients will be randomized to receive 5, 10 or 20 mL of 0.5% bupivacaine injected into their adductor canal. Strength following the block and recovery characteristics following TKA will then be evaluated including pain, strength and ability to participate in physical therapy.

4. Study population

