The subject will be met in the preoperative area by a staff anesthesiologist, who interviews and examines the subject. A full explanation of the neuraxial anesthetic and adductor canal block, including risks, benefits and alternatives, will be given and informed consent for anesthetic services obtained. Quadriceps motor strength and adductor strength will be assessed prior to any nerve blockade. Muscle strength will be assessed with the kio Sensor (Kio Inc., Madison, WI USA). The kio sensor is a force monitoring device that provides objective measurements of patient strength (traditional measurements or Manual Muscle Testing typically relies on subjective assessments by medical staff). To assess the subject's quadriceps and adductor strength, the kio sensor will be attached to the subject's ankle or upper leg and subject will be asked to forcefully extend the leg at the knee or adduct their leg. The kio Sensor is not currently commercially available and is currently in the development stage (see attached Phase I progress report – APPENDIX D). A sensory exam of the leg (temperature and pinprick) will also

be conducted prior to nerve blockade to determine baseline sensation of femoral, obturator and lateral femoral cutaneous nerves. For these tests, the jagged edges of a broken tongue depressor and alcohol swab will be used to produce pinprick and cold sensation. Subjects will be asked to report if sensation is normal, absent or decreased to both pinprick and cold.

From the subject's medical record the SF12 mental component and physical component, WOMAC and Knee Society Score, UCLA activity score, preoperative range of motion and degree of varus/valgus deformity will be collected. These scores and procedures are standard of care for all patients undergoing a TKA.

Adductor Canal Block Procedure:

An intravenous catheter will be placed, the subject will be transported to the block room or another room appropriate for provision of regional anesthesia and the subject will be pre-medicated with midazolam and/or fentanyl as needed at the discretion of the staff anesthesiologist.

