Adductor canal blockade will be performed with the assistance of ultrasound guidance following sedation with midazolam and fentanyl as deemed appropriate by the staff anesthesiologist. The adductor canal will be located in a mid-thigh position. A Stimuplex needle (B. Braun Medical Inc., Melsungen, Germany) will be inserted in-plane to the ultrasound probe until the tip of the needle is appropriately positioned.

Study Randomization:

Following negative aspiration, SSACNB volume will be randomized and subjects will receive 5, 10 or 20 ml of 0.5% bupivacaine will be incrementally injected. Randomization of the volume of bupivacaine will be determined by opening a sequential, pre-sealed envelope with the group assignment designated within. All studied volumes are well within the acceptable range for SSACNB.

15 minutes post-block placement:

A sensory examination will be done 15 minutes following adductor canal block with pin prick (sharp end of tongue depressor broken in two) and alcohol swab in distribution of femoral, obturator and lateral femoral cutaneous nerve. Motor examination of quadriceps and adductor strength will also be tested 15 minutes following adductor canal blockade.

During the Surgical Procedure:

Neuraxial anesthesia will be performed as normally accomplished prior to initiation of the surgical procedure. Generally, this involves the administration of a combined-spinal-epidural anesthesia with 2.5 – 3 ml 0.5% bupivacaine administered into the intrathecal space.

In the operating room and procedural suite, monitors will be applied to the subject per established American Society of Anesthesiology (ASA) guidelines. At a minimum, these include non-invasive monitoring of blood pressure by automated cuff, oxygen saturation via pulse oximetry, heart rate and rhythm by 3-lead continuous electrocardiographic (ECG) tracing, core body temperature and expired carbon dioxide concentration. Additional monitoring may be applied on a case-by-case basis as deemed appropriate by the attending anesthesiologist. Ongoing sedation with midazolam, fentanyl and propofol will be provided as deemed appropriate by the staff anesthesiologist.

The surgical team will inject 50 ml 0.125% bupivacaine with 30 mg ketorolac (when deemed to be clinically appropriate) into the joint and posterior knee at the conclusion of the surgical procedure.

Post-Procedure:

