Physical therapy will determine pain with physical therapy, quadriceps strength, passive flexion/extension range of motion, postoperative quadriceps strength, postoperative adductor strength, and 10 meter walk test (gait velocity) at 24 and 48 hours postoperatively. All measurements of strength will be done using the Kiiro Sensor. Based on physical therapy team experience, patients are currently able to ambulate 10 meters in approximately 45 seconds on postoperative day one with 20 ml of local anesthetic injected into the adductor canal. The physical therapy team feels that ambulation velocity is generally limited by weakness and pain. However, we do not currently know if decreasing the dose of local anesthetic injected into the adductor canal will result in improved ambulation resulting from increased strength or worsened ambulation performance secondary to increased pain.

Concomitant Medications:

Analgesic and anti-emetic requirements for block placement, intraoperatively, in PACU, at 24 hours, 48 hours and during course of hospitalization will be extracted from the patient's electronic medical record.

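### Section 2.2 lists variables fixed before randomization as secondary variables to compare, while the post-block strength test is not explicitly listed and has a 5 to 25 minute window

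*Combined protocol and SAP*

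**What the plan says.** Section 2.2 is headed as secondary outcomes and endpoints and begins "The secondary purposes of this study are to compare the following perioperative variables". Its pre/intraoperative group contains SF12, WOMAC and Knee Society, UCLA, preoperative range of motion, varus/valgus deformity, and preoperative quadriceps and adductor strength. These stand beside opioid consumption, sensory blockade and discomfort with the procedure. Postoperative quadriceps and adductor strength appear under the physical therapy variables.

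Strength is measured at three stages:

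- **Before the block.** Section 7: "Quadriceps motor strength and adductor strength will be assessed prior to any nerve blockade".
- **After the block, Visit 3.** Section 7: "Motor examination of quadriceps and adductor strength will also be tested 15 minutes following adductor canal blockade". The schedule of activities gives the tolerance: "15 minutes after adductor block placed +/- 10 mins".
- **After surgery.** Section 7 has physical therapy measure strength and "postoperative adductor strength, and 10 meter walk test (gait velocity) at 24 and 48 hours postoperatively".

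The study summary says the strength measurements are meant "to further evaluate the impact of volume of injection of local anesthetic into the adductor canal on motor strength". Section 3 says that strength after the block will be evaluated.

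Section 7 places randomization after needle placement and negative aspiration. Section 8 compares the groups by ANOVA and t-tests at 0.05 and promises a Bonferroni correction without saying which tests it covers.

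**The concern.** There are two linked problems.

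First, a variable whose value is settled before the envelope is opened cannot respond to the volume injected. Comparing it across arms as a secondary outcome can yield only chance differences, and a significant one could be reported as a finding. If the Bonferroni correction were spread over the whole 2.2 list, these items would also lower the threshold for outcomes that volume can affect.

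Second, the measurement closest to the mechanism has no explicit entry in that list. The strength tests at 24 and 48 hours follow surgery, neuraxial anesthesia and bupivacaine injected into the joint, and sections 7 and 8.1 report the physical therapy view that ambulation is limited by both weakness and pain. Visit 3 is the only post-block strength test before those influences. Section 2.2 does not say whether it is to be analysed as a raw value, as a change, or adjusted for the pre-block reading, and the permitted timing is wide. The volunteer study described in section 1.1 saw no strength change after 15 ml, so the effect sought may be small and avoidable noise unwelcome.

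**Working it through.** **The plan's own calculation.** The only computed figure in the plan is 16 per group for the 10 meter walk (difference 15 s, SD about 15 s, power 0.8, significance level 0.05). The two-sided normal formula gives n = 2 × (1.960 + 0.842)² × (15/15)² = 15.7, so 16. It reproduces, and nothing below bears on it.

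**Which bullets precede randomization.** Section 2.2 has 10 + 6 + 8 + 5 = 29 bullets.

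- Five are certain: SF12, WOMAC and Knee Society, UCLA, preoperative range of motion, deformity. The schedule collects the questionnaires and scores only at Visits 1 and 2, and section 7 takes all these items from the medical record under the heading for activities prior to the procedure.
- Two are uncertain: preoperative quadriceps and adductor strength. If they mean the test before any block, the count is seven. If they include the 15-minute test, which is also before surgery, they are partly post-randomization and the count stays at five.

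**Chance of a false positive, uncorrected.** Assume one independent test per bullet at 0.05:

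- five bullets: 1 − 0.95⁵ = 0.226, about 23%
- seven bullets: 1 − 0.95⁷ = 0.302, about 30%

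Positive correlation among the scores would tend to lower these figures. Several tests per bullet (two SF12 components, pairwise comparisons) would raise them.

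**If Bonferroni covered the 2.2 list.** This is an alternative to the previous case, not an addition to it. Assume one test per bullet:

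- all 29 bullets: 0.05/29 = 0.0017
- without five: 0.05/24 = 0.0021
- without seven: 0.05/22 = 0.0023

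At 0.05/29, the chance of any false positive among seven baseline bullets is 1 − (1 − 0.05/29)⁷, about 1.2%. The cost is then the stricter threshold for the other bullets, not spurious findings.

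**Visit 3 window.** 15 − 10 = 5 min and 15 + 10 = 25 min. The documents give no onset time for the block. As an illustration only, let the motor effect reach the fraction 1 − exp(−t/τ), with τ assumed to be 10 or 20 min:

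| τ (assumed) | at 5 min | at 25 min | ratio |
|---|---|---|---|
| 10 min | 39% | 92% | 2.3 |
| 20 min | 22% | 71% | 3.2 |

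These ratios compare the two extreme permitted readings. They are not a difference between arms.

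**Order of events.** "Neuraxial anesthesia will be performed as normally accomplished prior to initiation of the surgical procedure" fixes the neuraxial before surgery. That it also follows the Visit 3 test is inferred from the sequence of headings in section 7; it is not stated.

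**The case against.** Several stronger readings are tempting, and the documents do not support them.

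- *That the motor aim has no endpoint.* Section 2.2 names postoperative quadriceps and adductor strength, and section 3 says strength after the block will be evaluated. What is missing is an explicit post-block entry and its link to the pre-block value.
- *That Visit 3 is the only strength test free of surgery and spinal anesthesia, and a clean one.* The pre-block test is free of both as well. Visit 3 may also be affected by sedation: "Adductor canal blockade will be performed with the assistance of ultrasound guidance following sedation with midazolam and fentanyl as deemed appropriate by the staff anesthesiologist". A change from the pre-block reading would carry any sedation effect with it.
- *That the schedule and section 7 contradict each other.* Section 7 gives a nominal time and the schedule a tolerance. The protocol treats the 24 and 48 hour visits the same way, with ± 6 hours in the schedule only.
- *That the baseline items certainly use up the Bonferroni allowance.* Section 8 does not define the family. A correction for the pairwise comparisons of three volumes is at least as natural a reading.
- *That the window biases the volume comparison.* The tolerance is the same in every arm, and section 5.1 blinds the study member collecting pre- and postoperative data. Onset could differ by volume, but noise is the likelier result.

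The best general defence is that section 8.1 calls this a preliminary, hypothesis-generating study, and that the list may simply record what will be tabulated. That lowers the stakes. It does not remove the point, because 2.2 says the variables are to be compared and section 8 exempts none of them from testing.

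**Conclusion.** The point holds as a minor improvement. Five to seven of the 29 bullets in section 2.2 cannot be affected by the injection volume and do not belong among outcomes to compare. The 23% to 30% chance of a spurious difference applies only if they are tested uncorrected, once each and independently. The dilution from 0.05/22 or 0.05/24 to 0.05/29 applies only if the undefined Bonferroni family is this list.

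The post-block strength test is planned but not explicitly listed as a secondary outcome or related to its pre-block value. Its 5 to 25 minute window probably adds noise. The size of that noise is unknown because the documents contain no onset data. The primary endpoint and the sample size are untouched.

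**What to change.** 1. In section 2.2, move SF12, WOMAC and Knee Society, UCLA, preoperative range of motion and deformity to baseline characteristics, with pre-block strength. Describe them by arm or use them as covariates, outside significance testing and any Bonferroni family.
2. Replace the two preoperative strength bullets with post-block quadriceps and adductor strength, analysed as change from, or adjusted for, the pre-block reading. State which of the two will be used.
3. Record the actual minutes from the end of injection to the Visit 3 test. Where workflow allows, tighten the tolerance. The documents give no basis for prescribing a particular narrower window.
4. Note in the analysis plan that sedation given before the block may affect the post-block reading.

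The cost is protocol wording and, if the case report form does not already have it, one time field; the form (Appendix B) is not among the documents reviewed. Tightening the tolerance could lengthen the wait for some patients. The most possible within the existing window is 25 − 5 = 20 minutes, for a patient who would otherwise be tested at 5 minutes.

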1.1 Background

Postoperative analgesia for total knee arthroplasty (TKA) is incredibly important as it allows for effective physical therapy and ultimately ensures proper function of the implanted joint hardware.

Unfortunately, TKA is oftentimes associated with pain severe enough to limit participation in physical therapy which can ultimately result in prolonged hospitalizations and perhaps decreased joint function. A number of strategies have been reported to decrease the pain associated with TKA. Opioids are commonly utilized but they can be associated with a number of potential side effects including nausea, itching, respiratory depression, tolerance and the potential for abuse. Epidural analgesia has been utilized for postoperative analgesia but this strategy requires urinary catheterization (potential source of increased incidence of urinary tract infections), causes significant vasodilation with resulting hypotension and can cause bilateral lower extremity weakness that can undermine efforts at early physical therapy and rehabilitation. Femoral nerve blockade and femoral nerve catheters have the potential to decrease pain in the anterior knee but use of this technique is limited by incomplete analgesia and quadriceps motor weakness. Some groups have advocated for the substitution or addition of sciatic or obturator nerve blocks to femoral nerve blockade but this is at the expense of increased lower extremity weakness and little potential clinical benefit.¹⁻⁵

In an effort to balance the need for effective postoperative analgesia with the need to maintain lower extremity muscle strength for active participation in physical therapy, a number of groups have begun to evaluate the adductor canal block. The adductor canal is located in the middle 1/3 of the thigh and includes the saphenous nerve and nerve to the vastus medialis. The primary advantage to adductor canal blockade versus femoral nerve blockade is a potential sparing of the nerves to the quadriceps muscle and therefore preservation of lower extremity motor strength.⁶⁻⁸ Kwofie et al reported in a study of 16 volunteers that there was no change in quadriceps strength or hip adduction following the injection of 15 ml of local anesthetic. This is interesting as the obturator nerve is reported to travel within the adductor canal and is responsible for hip adduction. Kwofie et al also reported that SSACNB resulted in significantly decreased impairments with balance compared to a SSFNB.⁹

To this point, the majority of studies evaluating adductor canal blockade have focused on continuous techniques and little has been done to evaluate single shot techniques. Continuous techniques have the potential to extend analgesia but this is at the expense of increased cost, effort, resource utilization and potentially increased risk of infection.

The safety of CACNB technique was highlighted by a study by Henningsen et al where no cases of nerve injury related to analgesic technique were reported in a series of 97 patients.¹⁰ Andersen et al compared a CACNB vs control in 40 patients and found that the intervention group reported decreased pain and sleep disturbances while retaining the ability to ambulate soon after surgery.¹¹ Mudumbai et al evaluated 180 patients undergoing TKA and discovered that continuous adductor canal nerve blockade (CACNB) relative to continuous femoral nerve blockade (CFNB) resulted in greater ability to ambulate (37 m vs 6 m) on POD 1 and similar pain scores.⁸ Jaeger et al examined a similar group of 54 patients presenting for TKA and found that CACNB relative to CFNB resulted in decreased quadriceps weakness and no difference in pain, opioid consumption or weakness.¹² Jenstrup et al reported that, compared to placebo, CACNB resulted in decreased pain with flexion and opioid consumption.¹³ Only recently has a study comparing SSACNB and SSFNB been published. This study demonstrated that SSACNB resulted in decreased postoperative quadriceps weakness and similar pain control to SSFNB.¹⁴ Of interest, previous research has demonstrated that 15 ml 0.5% ropivacaine is required to produce ultrasound guided

femoral nerve blockade (including sensory and quadriceps motor weakness) but no such study has yet been done for the adductor canal block.¹⁵ It is possible that larger volumes of local anesthetic injected into the adductor canal could result in proximal spread of local anesthetic and increase quadriceps weakness and difficulty ambulating. It is also possible that decreased volumes of injection may result in inferior pain control and difficulties participating in physical therapy.

